### **8.3.2 Peripheral Neuropathy**

Signs/symptoms of peripheral neuropathy may include: hypoesthesia, hyperesthesia, paresthesia, discomfort, a burning sensation, neuropathic pain, or weakness.

If peripheral neuropathy is observed, additional serum/plasma samples may be drawn at the time of the event to evaluate drug concentration and ADA, as well as to assess levels of cytokines and/or other markers of inflammation.

Peripheral neuropathy is a known adverse event from MMAE-based ADCs and can be expected to occur with OBI-999. Therefore, specific assessment for signs and symptoms of peripheral neuropathy should be performed at each physical exam. Patients who develop peripheral neuropathy should be followed until resolution in order to define the time to resolution of the neuropathy.

Additionally, non-symptomatic patients will continue to be monitored for possible signs and symptoms of peripheral neuropathy as part of the Safety Follow-Up period.

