### **9.2      Procedures by Study Period**

Assessments and study procedures are to be performed as outlined in the Schedule of Assessments, [Table 9-1](#). The PK and ADA Sampling Schedules are provided in [Table 9-2](#) (Part A) and [Table 9-3](#) (Part B).

The Investigator may at his/her discretion arrange for a patient to have an unscheduled assessment, especially in the case of AEs that require follow-up or an AE considered by the Investigator to be possibly related to the use of study drug. The unscheduled visit page on the eCRF must be completed. Additional visits to follow-up positive ADA may happen after end of study ([Table 9-1](#)).

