**Table 9-1 Schedule of Assessments**

Study Procedure	Screening Visit	Treatment Period						EoS / ET	F/U
		Cycle 1					Cycle 2-35		
Cycle (C) #	-								
Cycle # and Day		C1D1	C1D2	C1D4	C1D8	C1D11	C1D15	D1	
Window period (days)	-28 to -1	-1*	±1	±3	±3	±3	±3	±3	±7
Informed consent a	X								
Demographics	X								
Eligibility screening	X	X							
Medical history b	X	X							
Physical examination c	X	X			X*		X	X	X
Height, weight d	X d	X					X	X	
Vital signs e	X	X					X	X	
Ophthalmology examination f	X						Q6wk for the first 6 months, then Q9wk thereafter f		X
ECOG g	X						X	X	
12-lead ECG h	X	X		X g				X	
Pregnancy testing i	X							X	
Tumor biopsy j	X								
Hematology and serum chemistry k	X	X			X		X	Every week for Cycles 2 and 3, then D1 of Cycles 4+	X
Coagulation and urinalysis l	X							D1 of each 21-day cycle l	X
Drug administration m		X						D1 of each 21-day cycle	
Pharmacokinetic sample n			See footnote n						
Immunogenicity (ADA) o		X						See footnote o	X
Radiology evaluations (CT or MRI) p	X							Q6wk for the first 3 months, then Q9wk thereafter	X
Concomitant medications		↔							
Adverse events		↔							→

Abbreviations: ADA = anti-drug antibody; D = Day; C = Cycle; CT = computed tomography; ECG = electrocardiogram; ECOG = Eastern Cooperative Oncology Group; EoS = End of Study; ET = Early Termination; F/U = follow-up; MRI = magnetic resonance imaging; Q6wk = every 6 weeks; Q9wk = every 9 weeks

EoS Visit is the safety follow-up visit, conducted  $28\pm 7$  days after the last OBI-999 dose. ET Visit lab assessments will be conducted for patients discontinuing study treatment, if last available tests are before 2 weeks.

\*The - 1 day window (1 day prior) for C1D1 is for safety laboratory assessments. Blood can be drawn 1 day prior to initiation of study drug infusion on C1D1. Safety laboratory results should be available and reviewed by the Investigator prior to the OBI-999 administration.

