Hematology: hematocrit, hemoglobin, erythrocyte count, white blood count, absolute counts of leukocytes, neutrophils, lymphocytes, monocytes, eosinophils, basophils, and platelet count.  
Serum chemistry: sodium, potassium, chloride, bicarbonate, blood urea nitrogen, creatinine, glucose, calcium, phosphorus, magnesium, total protein, albumin, alanine aminotransferase, aspartate aminotransferase, alkaline phosphatase, creatine kinase, lactate dehydrogenase, total bilirubin, and uric acid. Creatinine clearance will be calculated by Cockcroft Gault equation at screen visit, week 1 and EoS/ET.

I. Coagulation, and Urinalysis (Laboratory Assessments: [Table 12-1](#)). Blood draw and urine collection is prior to OBI-999 infusion. Only urinalysis will be collected at Day 1 of Cycles 2-35.

Coagulation: prothrombin time, activated partial thromboplastin time, and international normalized ratio.

Urinalysis: specific gravity, pH, protein, glucose, ketones, bilirubin, urobilinogen, blood, nitrite, leukocyte esterase as assessed by dipstick. A microscopic urinalysis (only if needed) evaluating white blood cells, red blood cells, epithelial cells, bacteria, cast and crystals

m. OBI-999 is given on Day 1 of each 21-day cycle until DLT, disease progression, unacceptable toxicity, or withdrawal of consent, whichever occurs earlier.

n. Pharmacokinetic: (for analysis of serum concentration of OBI-999 total antibody, ADC and free MMAE). Detailed sampling schedule in [Table 9-2](#) (Part A) and [Table 9-3](#) (Part B).

o. Immunogenicity studies (ADA) - ADA samples will be collected. Detailed sampling schedule in [Table 9-2](#) (Part A) and [Table 9-3](#) (Part B). For patients with persistent antibodies at end of study, an additional ADA sample will be collected at 4 months after the end of study visit.

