## **12.5 Adverse Events**

### **12.5.1 Adverse Events**

An AE is any symptom, physical sign, syndrome, or disease that either emerges during the study period or worsens during the study, regardless of the suspected cause of the event. All medical and psychiatric conditions (except those related to the indication under study) present at screening will be documented in the medical history eCRF. Changes in these conditions and new symptoms, physical signs, syndromes, or diseases should be noted on the AE eCRF during the rest of the study. Clinically significant laboratory abnormalities should also be recorded as AEs. Surgical procedures that were planned before the patient enrolled in the study are not considered AEs if the conditions were known before study inclusion; the medical condition should be reported in the patient's medical history.

Patients will be instructed to report AEs at each study visit. All AEs are to be followed until resolution or until a stable clinical endpoint is reached.

Each AE is to be documented on the eCRF with reference to date of onset, duration, incidence, severity, relationship to study drug, action taken with study drug, treatment of event, and outcome. Furthermore, each AE is to be classified as being serious or non-serious. Changes in AEs and resolution dates are to be documented on the eCRF.

For the purpose of this study, treatment emergent AEs will be collected starting from the time the patient receives the first dose of study drug (from Cycle 1 Day 1) until 28 days after the last dose of study drug. Follow-up of the AE, even after the date of therapy discontinuation, is required if the AE persists until the event resolves or stabilizes at a level acceptable to the Investigator.

Specific guidelines for classifying AEs by intensity (Grade) and relationship to study drug are given in Table 12-2 and [Table 12-3](#). The severity of AEs will be graded according to the NCI CTCAE version 5.0 (Grades 1 to 5).

When changes in the intensity of an AE occur more frequently than once a day, the maximum intensity for the event should be noted.

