### **12.5.3 Serious Adverse Event Reporting**

An SAE occurring during the study from the first dose of study treatment (Cycle 1 Day 1) to within 28 days of stopping the treatment must be reported to the contracted CRO and will be communicated to the Sponsor. Any such SAE due to any cause, whether or not related to the study drug, must be reported within 24 hours of occurrence or when the Investigator first becomes aware of the event. The Investigator must enter all SAE information into the electronic data capture (EDC) (preferred method), electronic mail (SAE Report Form), dedicated fax line or telephone line (emergency), to the Sponsor/contracted CRO.

If the Investigator contacts the contracted CRO by telephone, then a written report must follow within 24 hours and is to include a full description of the event and sequelae in the format detailed in the SAE reporting form.

The event must also be recorded on the standard AE eCRF. Preliminary reports of SAEs must be followed by detailed descriptions later on, including clear and anonymized photocopies of hospital case reports, consultant reports, autopsy reports, and other documents when requested and applicable. SAE reports must be made whether or not the Investigator considers the event to be related to the investigational drug.

Appropriate remedial measures should be taken to treat the SAE, and the response should be recorded. Clinical, laboratory, and diagnostic measures should be employed as needed in order to determine the etiology of the problem. The Investigator must report all additional follow-up evaluations to the contracted CRO within 10 calendar days. All SAEs will be followed until the Investigator and Sponsor agree the event is satisfactorily resolved or returns to the baseline condition.

Any SAE that is not resolved by the end of the study or upon discontinuation of the patient's participation in the study is to be followed until it either resolves, stabilizes, returns to baseline values (if a baseline value is available), or is shown to not be attributable to the study drug or procedures.

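### The SAE reporting duty ends 28 days after treatment, with no clause for a later-onset SAE considered related to OBI-999

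*Protocol*

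**What the plan says.** Protocol section 12.5.3 sets the duty. An SAE from the first dose onward "to within 28 days of stopping the treatment must be reported to the contracted CRO and will be communicated to the Sponsor". The clock follows in the next sentence: "Any such SAE due to any cause, whether or not related to the study drug, must be reported within 24 hours" of its occurrence or of the investigator learning of it. The closing paragraph provides for follow-up after the study, but its subject is "Any SAE that is not resolved by the end of the study", or at the patient's discontinuation from it.

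Section 12.5.1 stops collection of treatment-emergent AEs at the same point, "until 28 days after the last dose of study drug". SAP section 10.7.1 uses the same limit to define a treatment-emergent event.

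Several provisions can bring a patient into contact with the site after Day 28:

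- **Table 9-1:** "EoS Visit is the safety follow-up visit", set at 28 ± 7 days after the last dose.
- **Table 9-1, footnote o:** for patients with persistent antibodies, "an additional ADA sample will be collected at 4 months after the end of study visit".
- **Section 9.2:** "Additional visits to follow-up positive ADA may happen after end of study".
- **Section 8.3.2:** "Patients who develop peripheral neuropathy should be followed until resolution", with no upper time limit.

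**The concern.** A cut-off for SAEs of any cause is ordinary. In advanced cancer, most late serious events will come from the disease or the next therapy, and collecting them all would add little. What is missing is the usual exception for an event that the investigator attributes to the study drug.

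A site that follows section 12.5.3 exactly has no duty to report such an event if it starts after the window. The text does not bar a late report, but it gives no trigger, deadline or route, so sites may act differently. An event that is not reported cannot enter the sponsor's evaluation for expedited reporting (section 12.5.2) or the SAE tabulations that the Safety Review Committee receives (section 14.6).

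This matters more here because the drug is a first-in-human conjugate with an expected neurotoxicity that section 14.6 lists among cumulative toxicities. For reproductive risk the protocol already looks well past Day 28, since the inclusion criteria require contraception for at least 120 days after the last dose.

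**Working it through.** **1. Does any clause cover a new, related SAE with onset after the window?**

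| Provision (Protocol) | What it covers | New related SAE after the window? |
|---|---|---|
| 12.5.3, reporting duty | SAEs from first dose to 28 days after stopping treatment | No |
| 12.5.3, 24-hour clock | The SAEs just defined, whatever their cause | No; cause does not extend the time limit |
| 12.5.3, last paragraph | SAEs unresolved at end of study or at discontinuation | No; already open |
| 12.5.1 | Treatment-emergent AEs to 28 days after last dose; persisting AEs followed | No |
| 7.3 | Events that led to discontinuation | No; already open |
| 8.3.2 | Patients who already have neuropathy; symptom-free patients during Safety Follow-Up | Creates contact, not a reporting duty |
| 12.5.2 | Definition of seriousness and the sponsor's evaluation | Sets no reporting window |
| 12.5.4 | Pregnancy outcomes meeting SAE criteria | A late route, but not based on relatedness to OBI-999 |

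No row closes the gap. The pregnancy provision shows that a late SAE route is workable within this protocol.

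**2. When do the later contacts fall?** Assumption: stopping treatment in 12.5.3 means the last dose, as in 12.5.1. Months are converted at 30.4 days (SAP section 10.1).

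- End-of-study visit: 28 − 7 = Day 21 to 28 + 7 = Day 35. At the latest, 35 − 28 = 7 days past the cut-off.
- Antibody-persistence sample: 4 × 30.4 = 121.6 days after that visit.
  - Earliest: 21 + 121.6 = 142.6 days after last dose (142.6 / 30.4 = 4.7 months), which is 142.6 − 28 = 114.6 days past the cut-off.
  - Latest: 35 + 121.6 = 156.6 days after last dose (156.6 / 30.4 = 5.2 months), which is 156.6 − 28 = 128.6 days past the cut-off.
- Neuropathy follow-up has no end date to compute.

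**3. How much drug is left at Day 28?** Half-lives are from Protocol Table 4-1. The fraction remaining is 0.5^(28 / half-life), assuming simple first-order decay.

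| Analyte | Half-life (days) | 28 / half-life | Remaining |
|---|---|---|---|
| OBI-999, 1.2 mg/kg | 3.6 | 7.78 | 0.46% |
| MMAE, 1.2 mg/kg | 2.96 | 9.46 | 0.14% |
| OBI-999, longest at any dose (0.8 mg/kg) | 3.9 | 7.18 | 0.69% |
| MMAE, longest at any dose (0.8 mg/kg) | 3.51 | 7.98 | 0.40% |

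The 1.2 mg/kg row in Table 4-1 rests on 5 patients. Low serum levels make late-onset events less likely, but they do not exclude late expression of a cumulative toxicity.

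**The case against.** The strongest case is that little falls through the gap. The most foreseeable late toxicity is neuropathy. If it begins on treatment and worsens later, it is a change in an open AE, which section 12.5.1 requires to be documented and section 8.3.2 follows to resolution. Almost no drug remains in serum at Day 28. The visit window adds at most 7 days, and if stopping treatment means a discontinuation decision made after the last dose, the Day 35 visit could fall inside the reporting window. The late antibody contact is a blood sample in a subset of patients, with no safety assessment described.

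Other text also points the other way. Section 12.5.1 defines an AE by the study period, and section 6.1.3 includes follow-up in that period. SAP section 10.7.1 names a listing of post-treatment AEs. Sections 15.1.1 and 15.8 commit the study to federal regulations and GCP.

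The remedy can be questioned too. Table 12-3 lets an event count as possibly related when a connection seems unlikely but cannot be ruled out, which is a broad trigger with no time limit. The SAP's serious-event tables would still exclude late SAEs, and the sentence adds no new contact at which to detect them.

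Most of this stands as a limit on size; none of it supplies the missing duty. Documenting a change in an open AE does not cover a new event. The antibody sample stays outside the window unless treatment is declared stopped about 115 days or more after the last dose. The SAP listing is an output, not an instruction to sites, and it is not marked for the abbreviated report. General references to regulations and GCP give a site no trigger or deadline in the protocol itself, and their content cannot be checked from these documents. The breadth of the possibly-related category is a real cost and is counted as one below.

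**Conclusion.** The gap is real: no sentence in the protocol requires a site to report a new SAE, considered related to OBI-999, that starts more than 28 days after treatment stops. The protocol's own contacts extend up to 7 days past that point for the safety visit and about 115 to 129 days past it for patients with persistent antibodies, with no limit for patients being followed for neuropathy.

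The number of events affected cannot be derived from the documents and is probably small. The dates assume that stopping treatment means the last dose, and the residual-drug figures assume first-order decay. This is a change that should be made, not a flaw that undermines the trial; confidence is medium. The sponsor stopped the study on 10 November 2023 (SAP section 3), so the remaining benefit in this trial depends on whether any patient is still being followed, which the documents do not say.

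**What to change.** Keep the 28-day window for SAEs of any cause and add one sentence to Protocol section 12.5.3:

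> Any SAE that the Investigator considers at least possibly related to OBI-999 must be reported within 24 hours of awareness, regardless of the time since last dose.

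The cost is one protocol sentence and matching eCRF guidance. No visit, procedure or staff is added. The downside is some late reports to process after end of study. That number is probably small but cannot be estimated, and the wide definition of possibly related will push it up. The planned treatment-emergent tables need not change, because the aim is to get the event to the sponsor and the Safety Review Committee.

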### **12.5.4 Pregnancy**

Female patients of child-bearing potential must have a negative pregnancy test at the screening (serum) and the end of study/early termination visit (serum / urine). Following administration of study drug (from Cycle 1 Day 1 until 28 days after the last dose), any known cases of pregnancy in female patients will be reported until the patient completes or withdraws from the study. The pregnancy will be reported immediately by phone and by faxing/emailing a

completed Pregnancy Report to the Sponsor (or designee) within 24 hours of knowledge of the event. The pregnancy will not be processed as an SAE; however, pregnancies should be considered important medical events and should be reported on the pregnancy report form/SAE form within 24 hours of the first learning of the event for further processing. The pregnancy will be categorized as a non-serious AE in the safety database for tracking purposes. The Investigator will follow the patient until completion of the pregnancy and must assess the outcome in the shortest possible time but not more than 30 days after completion of the pregnancy. The Investigator should notify the Sponsor (or designee) of the pregnancy outcome by submitting a follow-up Pregnancy Report. If the outcome of the pregnancy meets the criteria for immediate classification of an SAE (e.g., spontaneous or therapeutic abortion [any congenital anomaly detected in an aborted fetus is to be documented], stillbirth, neonatal death, or congenital anomaly), the Investigator will report the event by phone and by faxing a completed SAE form to the Sponsor (or designee) within 24 hours of knowledge of the event and the SAE reporting process will be followed.

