### **6.1.3 Duration of Study**

The study (Parts A and B) will include a screening period (up to 28 days), a treatment period, and a follow-up period.

Patients will continue to receive treatment with OBI-999 until disease progression, unacceptable toxicity, consent withdrawal, or for up to 35 cycles (approximately 2 years), whichever occurs first. Patients will be followed up to the 24-week scheduled response assessment for the purposes of counting objective responses for Simon's two-stage design success criteria.

The safety follow-up visit will be conducted 28 days after the last dose of study treatment.

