# 7 Selection and Withdrawal of Patients

## 7.1 Inclusion and Exclusion Criteria

### 7.1.1 Inclusion Criteria

Patients must meet all of the following criteria in order to be included in the study (for both Parts A and B unless specified otherwise):

1. Male or female patients, 18 years of age or older at the time of consent.
2. Provide written informed consent prior to performing any study-related procedure.
3. Histologically or cytologically confirmed patients with advanced solid tumors.

4. Patients must have been treated with established standard-of-care therapy, or physicians have determined that such established therapy is not sufficiently efficacious, or patients have declined to receive standard-of-care therapy. In the latter case, the informed consent must state the effective therapies the patient is declining.
5. Measurable disease (i.e., at least one measurable lesion per RECIST 1.1) ([Eisenhauer, et al., 2009](#)).
6. Eastern Cooperative Oncology Group (ECOG) performance status of 0 or 1 ([Oken, et al., 1982](#)).
7. Adequate organ function defined as:
  - a. Hepatic:
    - i. Serum ALT  $\leq 3 \times$  upper limit of normal (ULN),  $\leq 5 \times$  ULN in the presence of liver metastases
    - ii. Serum AST  $\leq 3 \times$  ULN,  $\leq 5 \times$  ULN in presence of liver metastases
    - iii. Serum bilirubin  $\leq 1.5 \times$  ULN (unless due to Gilbert's syndrome or hemolysis)
  - b. Renal:
    - i. Creatinine clearance  $> 50$  mL/minute using Cockcroft Gault equation
  - c. Hematologic:
    - i. Absolute neutrophil count  $\geq 1,500/\mu\text{L}$
    - ii. Platelets  $\geq 100,000/\mu\text{L}$
    - iii. Hemoglobin  $\geq 8 \text{ g/dL}$
8. Patient is willing and able to comply with all protocol-required assessments, visits, and procedures, including a pretreatment tumor biopsy. Archival tumor biopsies are acceptable at baseline.
9. Females of childbearing potential must have negative serum pregnancy test prior to starting study therapy, and agree to use a reliable form of contraceptive during the study treatment period and for at least 120 days following the last dose of study drug.  
Patient not of childbearing potential (i.e., permanently sterilized, postmenopausal) can be included in study. Postmenopausal is defined as 12 months with no menses without an alternative medical cause.  

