Male patients must agree to use an adequate method of contraception during the study treatment period and for at least 120 days following the last dose of study drug.
10. Cannot be breast feeding.
11. Patients with human immunodeficiency virus (HIV) infection are eligible if CD4+ T-cell counts  $\geq 350 \text{ cells}/\mu\text{L}$ ; patients on antiretroviral therapy (ART) should be on an established dose for at least 4 weeks and have an HIV viral load less than 400 copies/mL prior to enrollment.
12. Patients with serological evidence of chronic hepatitis B virus (HBV) infection are eligible if they have an HBV viral load below the limit of quantification with or without concurrent viral suppressive therapy.
13. Patients with a history of hepatitis C virus (HCV) infection should have completed curative antiviral treatment and have a viral load below the limit of quantification.

14. Patients in Part B (Cohort-Expansion) must have documented Globo H H-score  $\geq 100$  from a qualified laboratory IHC assay in one of the following tumor types to be enrolled in the respective cohort:

- Cohort 1: Pancreatic cancer
  - Histopathologically confirmed patients with metastatic adenocarcinoma of the pancreas.
- Cohort 2: Colorectal cancer
  - Histopathologically confirmed patients with metastatic colorectal adenocarcinoma.
- Cohort 3: Basket (any solid tumor type other than those included in Cohorts 1 and 2)
  - Histologically or cytologically confirmed patients with advanced solid tumors.

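### The duty to report known pregnancies ends 28 days after the last dose, while contraception is required for at least 120 days, and partner pregnancies are not covered at all

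*Protocol*

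**What the plan says.** **Reporting.** Protocol 12.5.4 (Pregnancy) sets the window as "from Cycle 1 Day 1 until 28 days after the last dose". The same sentence limits the duty by person and by study status: "any known cases of pregnancy in female patients will be reported until the patient completes or withdraws from the study". A case within the window goes to the sponsor within 24 hours and is followed to its outcome.

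**Contraception.** Inclusion criterion 9 (Protocol 7.1.1, repeated in the synopsis) requires females of childbearing potential to use a "reliable form of contraceptive during the study treatment period and for at least 120 days following the last dose of study drug". The same minimum applies to men: "Male patients must agree to use an adequate method of contraception during the study treatment period and for at least 120 days" after the last dose.

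**End of study.** Protocol 6.1.3 states: "The safety follow-up visit will be conducted 28 days after the last dose of study treatment". The notes to Table 9-1 make this the end-of-study visit ("EoS Visit is the safety follow-up visit, conducted" at 28±7 days). The last scheduled pregnancy test is at end of study or early termination.

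**The concern.** Safety and tolerability are a primary objective, and OBI-999 carries an antimitotic payload. Section 12.5.4 treats pregnancies as important medical events with a 24-hour reporting deadline. Yet for most of the post-dose period in which patients are asked to avoid conception, a site that learns of a pregnancy has no duty to tell the sponsor. The protocol gives no reason for using a shorter period for reporting than for contraception.

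Men are a second part of the same gap. They carry the same contraception requirement as women, but 12.5.4 mentions only female patients. The reproductive effects described in Protocol 4.3.5 are in male rats: smaller testes with degenerative findings after single doses of 10 or 30 mg/kg, and seminiferous tubule degeneration and hypospermia at 10 mg/kg/dose and above on repeat dosing.

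What is at stake is pregnancy information on a new agent that could reach a site and go no further.

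**Working it through.** The plan states no figure on this point, so there is nothing to reproduce. The check compares time windows and then looks for another route that would close the gap.

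**Inputs**
- Contraception after last dose: at least 120 days (criterion 9, both sexes).
- Pregnancy reporting after last dose: 28 days (12.5.4).
- End-of-study visit: day 28±7, so day 21 to day 35 (Table 9-1 notes).

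**Gap, using the stated 28-day window**
- Contraception period − reporting period = 120 − 28 = 92 days (days 29 to 120).
- As a share of calendar days: 92 / 120 = 76.7%.

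**Gap, if reporting ends at the actual end-of-study visit**
- Visit on day 35: 120 − 35 = 85 days.
- Visit on day 21: 120 − 21 = 99 days.

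Criterion 9 sets 120 days as a minimum, so these figures are minimum gaps for the visit timing shown.

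**Does anything else close the gap?**

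| Possible route | Where | Covers a pregnancy first known after day 28 or end of study? |
|---|---|---|
| Adverse event collection | Protocol 12.5.1 | No; stops 28 days after last dose |
| Serious adverse event reporting | Protocol 12.5.3 | No; the duty runs "from the first dose of study treatment (Cycle 1 Day 1) to within 28 days of stopping the treatment must be reported" |
| Congenital anomaly as a serious event | Protocol 12.5.2 | No; subject to the same 28-day window |
| Follow-up to pregnancy outcome | Protocol 12.5.4 | No; applies to a pregnancy already reported |
| Pregnancy testing | Table 9-1, 12.5.4 | No; last test at end of study or early termination |
| Contact 4 months after end of study | Table 9-1 notes, 12.7 | No; an antibody sample, only for patients with persistent antibodies |
| SAP | 10.7.1, 10.8.2 | No; 28-day window for treatment-emergent events, and a listing of pregnancy test results |

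None of these extends the duty.

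**Partners of male patients.** Section 12.5.4 does not cover them during treatment or afterwards. The 92-day figure does not measure this part: for partners, the whole treatment period and the full 120 days are uncovered.

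**After reconciliation.** If the reporting duty ran for the same post-dose period as the contraception requirement, the uncovered interval would fall from 92 days to 0.

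**The case against.** The strongest reply is that the two sections do different jobs. Criterion 9 says what patients agree to do; 12.5.4 says what sites must report. Both can be followed in full, and the 28-day window matches adverse event collection, serious adverse event reporting, the safety follow-up visit and the SAP's definition of treatment-emergent events. This stands: a reader might infer that the sections contradict each other, and they do not. It does not remove the gap, because complying with both still leaves known pregnancies outside any reporting duty.

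Three other inferences are tempting and go too far.

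- **That the protocol declares a 120-day period of reproductive risk.** It does not use that idea. The 120 days is a contraception requirement, and its link to risk is inferred.
- **That 77% measures the safety gap.** It is a share of calendar days and gives day 29 the same weight as day 120. The longest half-life in Table 4-1 is 3.9 days, for OBI-999 (Part A, few patients). On that figure 28 / 3.9 ≈ 7.2 half-lives have passed by day 28, and 0.5^7.2 ≈ 0.7% remains. This does not show which window is right, but it rules out reading a share of days as a share of risk.
- **That the rat findings bear on pregnancies in female patients.** Protocol 4.3.5 describes reproductive effects in males only, at 10 mg/kg and above, with a no-effect level of 3 mg/kg. They support attention to partner pregnancies more directly than a longer window for women.

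It is also fair to say that a longer window may find few cases. Section 12.5.4 covers known pregnancies, and after the end-of-study visit there is almost no scheduled contact through which a site would learn of one. The documents give no expected number of pregnancies in this population.

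**Conclusion.** The gap is real and modest. As written, about 92 calendar days of the required contraception period carry no duty to report a known pregnancy in a female patient (85 to 99 days if reporting ends at the actual end-of-study visit). Partner pregnancies are not covered at any time.

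The figures assume that the 120-day minimum applies and that the patient reaches the end-of-study visit within its window. The absence of a duty does not forbid a site from reporting. The point is one of safety reporting only and does not affect the response analysis or the Simon design.

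The documents do not support calling this a contradiction, or reading the calendar gap as a measure of harm. They also do not settle which of the two durations is right. Section 3 of the SAP records that the sponsor stopped the study on 10 November 2023. The practical value now lies in any remaining post-dose follow-up, in stating the limits of pregnancy ascertainment in the abbreviated report, and in any later protocol that reuses this text.

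**What to change.** Reconcile Protocol 12.5.4 with inclusion criterion 9 (7.1.1 and the synopsis) so that the duty to report known pregnancies runs for the same period after the last dose as the contraception requirement. The sponsor should settle that period and give the reason for it. In the same section, say whether the end-of-study visit also ends the reporting duty, since the current sentence ties it both to day 28 and to study completion.

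Address pregnancies in partners of male patients explicitly. If they are included, say how the information would be obtained, because partners are not trial participants.

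The cost is protocol wording. Reporting stays passive, with no added visits or tests. The downside is that sites accept reports for longer, and ascertainment after the end-of-study visit stays limited because sites would report only what they happen to learn. The abbreviated report should state that limit.
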